## **6. MODIFICATIONS**

### **6.1. Modifications from the Approved Clinical Study Protocol**

Protocol Amendment 5 - change the primary endpoint from CFB Day 84 on HD-CAB composite score to CFB Day 84 SDMT, upgraded some secondary endpoints to key secondary endpoints, [REDACTED] and clarify the plan to conduct database lock in two parts. The SAP was adjusted to incorporate the changes described above.

### **6.2. Modifications from the Approved Statistical Analysis Plan**

This is the first version of the SAP for the final analysis.

### **6.3. Modifications from the Approved DMC Charter**

Not applicable.

## 7. ANALYSIS SETS

### 7.1. Full Analysis Set

The Full Analysis Set (FAS) is defined as all randomized participants who initiate IP and have baseline and at least 1 post-baseline efficacy evaluation. FAS will be used to analyze the efficacy data (participants will be analyzed according to the treatment group randomized to).

### 7.2. [REDACTED]

[REDACTED]

[REDACTED]

[REDACTED]

[REDACTED]

[REDACTED]

[REDACTED]

[REDACTED]

[REDACTED]

### 7.3. Safety Set

The Safety Set (SS) is defined as all participants who were administered IP (participants will be analyzed according to the treatment they received). The SS will be used to describe the safety data.

### 7.4. Other Analysis Sets

The Randomized Set is defined as all participants who have been randomized.

[REDACTED]

[REDACTED]

[REDACTED]

## 8. STATISTICAL ANALYSIS

### 8.1. General Considerations

Continuous data will be summarized in terms of the number of participants, mean, standard deviation (SD), minimum, and maximum. The minimum and maximum will be reported to the same number of decimal places as the raw data recorded in the database. The mean and median will be reported to one more decimal place, and the SD (and the standard error [SE], if applicable) will be reported to two more decimal places than the raw data recorded in the database. In general, the maximum number of decimal places reported will be four for any summary statistic. Any values that require transformation to standard units (metric or SI) will be converted with the appropriate corresponding precision.

Categorical data will be summarized in terms of the number of participants providing data at the relevant time point (n), frequency counts and percentages. Percentages will be reported to one decimal place unless otherwise specified. Any planned collapsing of categories will be detailed in the SAP text and the data displays.

Percentages will not be presented for zero counts. Percentages will be calculated using the number of participants (n) in the respective analysis set and/or in specific treatment group as the denominator. A missing category shall be included only for categorical variables where no data is available. The missing category will be omitted if there are no missing values for that variable.

For the laboratory results that are “ $\leq x$ ” or “ $\geq x$ ”, where x is a number as collected in the data, the numeric part of the result will be used in the calculation in the summary tables. If a laboratory value contains ‘y <’ then y minus 0.1 for values measured to the first decimal place, 0.01 for values measured to the second place, 0.001 for values measured to the third decimal place, and so on, will be used for the analysis. If a laboratory value contains ‘z >’ then z plus 0.1 for values measured to the first decimal place, 0.01 for values measured to the second place, 0.001 for values measured to the third decimal place, and so on, will be used for the analysis. The same is true if the result is presented as below limit of quantification (BLQ) and a lower limit of quantification (LLOQ) value is provided – LLOQ value will be used for calculation in the summary tables. The actual results as collected will be displayed in the listings.

P-values greater than or equal to 0.0001, in general, will be presented to four decimal places. P-values less than 0.0001 will be presented as “<0.0001”. P values greater than 0.9999 will be presented as “>0.9999”.

Confidence intervals will be presented to one more decimal place than the raw data.

All summaries and figures will be provided by treatment group – either by randomized treatment or actual treatment received depending on the analysis set being used. Treatment groups are presented as: SAGE-718 or Placebo.

Participants who are randomized to 1.2 mg treatment and received 0.9 mg dose due to dose reduction will be summarized under one treatment group. For efficacy data analysis, participants’ data are analyzed by randomized treatment. For safety data analysis, participants’ data are analyzed per the actual treatment received, and this is determined as

follows: if a participant received any dose of SAGE-718 at any point of time, the participant is assigned to actual treatment of SAGE-718.

All participant data, including those derived, to support tables and figures will be presented in the participant data listings. In general, the participant data listings will be sorted by participant number and assessment visit and date (and time, if applicable). The treatment will be identified for each participant.

General definitions are provided below:

- Baseline is defined as the last non-missing measurement prior to the first dose of IP, unless stated otherwise. If the time of an assessment is collected, baseline will be the latest assessment prior to first dose of IP administration time; if the time of an assessment is not collected, the assessment on Day 1 is assumed to be prior to dosing if the protocol mentions that this assessment needs to be before dosing or it is collected as “pre-dose”.
- Study day 1 is defined as the date of randomization for untreated randomized participants or the date of first dose for treated participants.
- Study Day will be calculated relative to the date of randomization for untreated randomized participants and relative to the date of first dose for treated participants.

If event is prior to randomization or the first dose, then study day is calculated as:

Date of Event – Date of Randomization or First Dose

If event is after randomization or the first dose, then study day is calculated as:

Date of Event – Date of Randomization or First Dose + 1

## **8.2. Background Characteristics**

### **8.2.1. Participant Disposition**

This analysis will be based on all screened participants (i.e., all participants who have signed an informed consent).

A disposition of all participants who enter the study will be provided, from screening to study completion. The summaries of participant disposition of all participants will include:

- Number of participants screened
- Number of participants screen-failed
- Number of participants randomized
- Number of participants randomized but not treated
- Number and percentage of participants received at least one dose of IP
- Number and percentage of participants completed full treatment period of IP
- Number and percentage of participants discontinued from IP and primary reason for premature IP discontinuation

- Number and percentage of participants completed the study (completed Day 112 visit)
- Number and percentage of participants who had dose reduction before Day 28
- Number and percentage of participants discontinued from the study and primary reason for premature study discontinuation
- Number and percentage of subjects who were randomized to placebo but received SAGE-718

All percentages will be calculated based on the participants from the Safety Set. Treatment arm assignment will be according to the randomized treatment. In addition, a summary of analysis sets including Safety Set, FAS, [REDACTED] will be provided for participants randomized.

If a participant is rescreened because the participant has been a screen failure the first time, the status of the participant will be determined from the second screening. In the count of screened participants, this participant will be counted only once.

Listings by treatment group will be provided for disposition of participants: screen failures, inclusion/exclusion criteria, completion and discontinuation from study treatment and study participation, and inclusion in analysis sets.

Summary of analysis sets including Safety Set, FAS, [REDACTED] will be provided for participants from Randomized Set.

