### 13.1. Data Analysis Sets

The Randomized Set will include all participants who have been randomized.

The Safety Set will include all participants who were administered IP and will be used to describe the safety data.

The Full Analysis Set (FAS) will include all participants who initiate IP and have baseline and at least 1 postbaseline efficacy evaluation.

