## 5.2. Sample Size and Study Power

The study is designed to detect a difference between placebo and the SAGE-718 group in the change from baseline to Day 84 for the primary endpoint, SDMT score. Using a 2-sided test at an alpha level of 0.05, a sample size of approximately 71 evaluable participants per treatment group would provide 90% power to detect a difference of 4 points between SAGE-718 and placebo arms in the change from baseline to Day 84 in SDMT values, assuming that the SD of the change from baseline in SDMT is 7.3 points.

Assuming a 20% dropout and a 1:1 randomization ratio, approximately 178 randomized participants (89 per treatment group) will be required to obtain 71 evaluable participants per treatment group. Evaluable participants are defined as those randomized participants who receive IP and have a valid baseline and at least 1 postbaseline SDMT assessment.

Additional participants may be randomized to ensure a sufficient number of evaluable participants or if the dropout rate is higher than 20%.

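### Disposition percentages are taken on the Safety Set, so the dosed percentage is always 100% and the study completion and discontinuation rates leave out anyone lost before the first dose

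*SAP*

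**What the plan says.** SAP 8.2.1 opens with the widest possible population: "This analysis will be based on all screened participants". It then lists rows running from screening to study completion, with arms assigned by randomized treatment. One row is "Number and percentage of participants received at least one dose of IP". Others give the number and percentage completing the study (the Day 112 visit) and discontinuing from it, with the primary reason. Participants randomized but never treated appear as a count without a percentage. The denominator rule admits no exception: "All percentages will be calculated based on the participants from the Safety Set".

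SAP 7.3 defines the set: "The Safety Set (SS) is defined as all participants who were administered IP". Protocol 13.1 agrees: "The Safety Set will include all participants who were administered IP and will be used to describe the safety data". SAP 7.4 also provides a wider set: "The Randomized Set is defined as all participants who have been randomized". SAP 8.2.1 uses that wider set for a separate summary of analysis sets, but not for the disposition percentages. Protocol 13.3 asks for the number enrolled and the percentage who discontinued from the study.

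**The concern.** A disposition table lets the reader follow randomized participants and see, by arm, how many were lost and when. A denominator restricted to dosed participants cannot show losses between randomization and first dose. One row becomes the Safety Set divided by itself. Study completion and discontinuation become rates among the dosed, in a table described as covering everyone who enters the study.

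The SAP expects that the case can arise: 8.2.1 has a row for it, and 8.1 defines Study Day 1 separately for randomized participants who were never treated. Disposition is also where such losses should be visible, because the FAS requires that IP was started and the demographic summaries use the Safety Set and the FAS. At stake is the clarity of the attrition figures, not any inference about treatment.

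**Working it through.** **Scale of the trial.** The disposition section states no figure, so the sample size in SAP 5.2 sets the scale. With a difference of 4, SD 7.3, two-sided alpha 0.05 and 90% power, the normal approximation gives 2 × (1.960 + 1.282)² × 7.3² / 4² = 70 per arm. At 71 per arm the noncentral t power (noncentrality 4 / (7.3 × √(2/71)) = 3.26, 140 df) is 0.900. Then 71 / 0.8 = 88.75, rounded up to 89 per arm, or 178 in total. The plan's figures reproduce.

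**Inputs.** N = 178 randomized (SAP 5.2). The documents do not give u, the number randomized but never dosed; it is assumed to lie between 0 and 9. D, all study discontinuations including the u never dosed, is assumed to be 36 and held fixed. The Safety Set has S = N − u participants.

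**Formulas.**
- Dosed: S/S under SAP 8.2.1; S/N on the Randomized Set.
- Discontinued from the study: (D − u)/S under SAP 8.2.1 if numerator and denominator are both restricted to the Safety Set; D/N on the Randomized Set.

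| u | S | Dosed, Safety Set | Dosed, Randomized Set | Discontinued, Safety Set | Discontinued, Randomized Set | Gap (points) |
|---|---|---|---|---|---|---|
| 0 | 178 | 100.0% | 100.0% | 36/178 = 20.2% | 20.2% | 0 |
| 1 | 177 | 100.0% | 99.4% | 35/177 = 19.8% | 20.2% | 0.45 |
| 2 | 176 | 100.0% | 98.9% | 34/176 = 19.3% | 20.2% | 0.9 |
| 5 | 173 | 100.0% | 97.2% | 31/173 = 17.9% | 20.2% | 2.3 |
| 9 | 169 | 100.0% | 94.9% | 27/169 = 16.0% | 20.2% | 4.2 |

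Study completion moves by the same amount the other way: with u = 2 it is 142/176 = 80.7% instead of 142/178 = 79.8%. (That 142 is N − D under the assumption; it matches the evaluable target only by coincidence.)

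**Numerator left unrestricted.** If never-dosed participants stayed in the numerator while the denominator remained S, the rate would be D/S: 36/177 = 20.3% for u = 1 and 36/176 = 20.5% for u = 2, which is 0.1 and 0.2 points too high. Across both readings the gap for u = 1 or 2 is therefore about 0.1 to 0.9 points. Neither reading returns the rate among randomized participants once u exceeds zero.

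**By arm.** The table is by arm, so an imbalance shows more. If both never-dosed participants were in one arm of 89, with 18 discontinuations assumed there, the rate is 18/89 = 20.2% on randomized participants and 16/87 = 18.4% on the Safety Set.

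**The case against.** Several points on the other side stand.

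- *A valid conditional rate.* Basing the percentages on Safety Set participants most naturally restricts numerator and denominator alike. The result is a proper rate among the dosed. The objection is to what it leaves out, not that it is miscalculated.
- *Largely recoverable.* The same section provides an analysis-set summary, including the Safety Set and FAS, for the Randomized Set, so the dosed fraction is already shown there. The counts of randomized and never-treated participants give it too. The discontinuation rate among randomized participants can be rebuilt only if the reader knows whether never-dosed participants are among the counted discontinuations, and SAP 8.2.1 does not say.
- *Few such participants are likely.* Protocol 10.6 and SAP Appendix A place randomization on Day 1, and the Day 1 dose is supervised in clinic. That leaves little time for loss before dosing, so 9 of 178 is an extreme case.
- *Most rows are sound.* IP completion, IP discontinuation and dose reduction belong on a dosed denominator. So does the row for placebo participants who received SAGE-718.

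Two stronger readings are tempting and are not supported. A reader might infer that the reported discontinuation rate would be misjudged against the planned 20%, since SAP 5.2 says "Assuming a 20% dropout and a 1:1 randomization ratio, approximately 178 randomized participants (89 per treatment group) will be required". That 20% is the loss from randomized to evaluable, and evaluable means dosed with a valid baseline and at least one post-baseline SDMT. A participant who leaves after a post-baseline SDMT is evaluable but has still discontinued the study, so the two quantities differ on any denominator. A reader might also infer that completed and discontinued percentages will sum to more than 100%. That requires all randomized participants in the numerator over dosed participants in the denominator, a mixture that the SAP does not state.

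**Conclusion.** The point holds as a minor reporting matter. By the SAP's own definitions the dosed percentage is 100% and carries no information, and the study completion and discontinuation percentages exclude losses before the first dose. With no never-dosed participants nothing changes. With 1 or 2 of 178 never dosed, the pooled discontinuation rate moves by about 0.1 to 0.9 percentage points. That size rests on the assumed 36 total discontinuations, on every never-dosed participant counting as one of them, and on the choice of numerator reading; the documents supply none of these. The estimand, FAS, primary model, alpha and power are unaffected.

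**What to change.** Replace the single denominator sentence in SAP 8.2.1 with a two-part rule:

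- Use the Randomized Set, by randomized arm, for participants who received at least one dose, were randomized but not treated (adding a percentage to that count), completed the study, and discontinued from the study, with reasons. State that a randomized participant who is never dosed counts as a study discontinuation.
- Use randomized participants who received IP, by randomized arm, for IP completion, IP discontinuation with reasons, and dose reduction.

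The cost is a short SAP edit and a change of denominator in one table. No new data are needed. The reported study discontinuation rate may come out slightly higher than under the present rule.

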### **8.2.2. Protocol Deviations**

Protocol deviations will be classified as “major” or “minor” on ongoing basis by the clinical study team and sponsor and documented separately from the SAP.

Major protocol deviations are defined as those deviations from the protocol likely to have an impact on the participant’s right, safety, well-being, and/or the validity of the data for analysis. Minor protocol deviations include all deviations from the protocol excluding the major protocol deviations.

Major protocol deviations and any action to be taken regarding the exclusion of participants or affected data from specific analyses are defined in the project-specific Protocol Deviation Specification.

The study team will identify the major protocol deviations related to efficacy or that may have impact on efficacy to determine the participants in the FAS to be excluded from the [REDACTED] prior to the first database lock in a blinded fashion. (Some major protocol deviations may not lead to participants’ data being excluded from the [REDACTED].) The [REDACTED] will be updated before the final database lock if needed.

The number and percentage of participants with a major protocol deviation in the FAS will be summarized by randomized treatment group. A by-participant listing of all protocol deviations will also be provided.

In addition, COVID-19 related protocol deviations such as remote telephone/video visit/assessment, home healthcare visit, missed visit/assessment, out of window

visit/assessment, safety reporting, IP administration, and other will be documented and provided as a separate listing.

### **8.2.3. Demographics and Baseline Characteristics**

This analysis will be based on the Safety Set and FAS.

Demographic characteristics (age, race, sex, ethnicity, childbearing status, civil/marital status, highest level of education, years of education, current employment status, and total years of employment [employment history]) and baseline characteristics, such as height (cm), weight (kg), body mass index (BMI, kg/m^2), SDMT score, UHDRS – IS/ [REDACTED] CAG expansion, CAP (CAG-Age-Product, truncation of Trail Making Test B value, (complete within 240 sec: yes/no ), previous ASO use and use of Antidopaminergic Medications (ADM, see Appendix D for details) will be summarized by treatment group (randomized for FAS and actual for Safety Set) and overall.

Baseline subgroups will be summarized for the following categories:

- Age ( $\leq 50, > 50$ )
- Race (Black or African American, White, Other)
- Sex (Male, Female, Unknown/Undifferentiated)
- BMI ( $\leq 18.4, 18.5-24.9, 25-29.9, \geq 30$  kg/m^2)
- Country (US, Rest of World)
- Baseline MoCA score ( $< 18, \geq 18$ )
- Baseline UHDRS – Independent scale ( $< 80, \geq 80$ )
- CAP ( $< 100, \geq 100$ )
- [REDACTED]
- [REDACTED]
- [REDACTED]
- Baseline Symbol Digit Modalities Test (SDMT) ( $< M, > M$ , where M=Mean value at Baseline in FAS)
- Baseline Trail Making Test B (complete within 240 sec: yes/no)
- Previous use of ASO drug (Yes / No)
- Use of ADM (Yes/No)
- Use of Anti-Chorea Medication (Yes / No)
- Use of Anti-Psychotic Medication (Yes / No)

If height was collected in inches the following formula will be used to convert it to cm: Cm = Inch \* 2.54. If the value for CAP is missing at baseline, it should be calculated as CAP=AGE  $\times$  (CAG – 30) / 6.49. BMI will be calculated as weight (kg)/height (m^2).

By-participant listing of demographic and other baseline characteristics will also be provided.

#### **8.2.4. Medical History**

This analysis will be based on the Safety Set.

Medical history at screening will be coded using the Medical Dictionary for Regulatory Activities (MedDRA) Version 25.1 and summarized using system organ class (SOC) and preferred term (PT) on Safety Set by actual treatment group.

In addition, participant's COVID-19 history will be collected via medical history eCRF page and will be coded by MedDRA.

By-participant listing of medical history will also be provided.

#### **8.2.5. Prior and Concomitant Medications/Procedure**

This analysis will be based on the Safety Set.

Medications/procedures will be recorded at each study visit during the study and will be coded using World Health Organization-Drug dictionary (WHODrug-Global-B3) September 2022 B3. All medications/procedures taken within 60 days prior to informed consent through the duration of the study will be recorded. Those medications/procedures started and stopped prior to the initiation of the start of IP will be denoted "Prior". Those medications/procedures taken prior to the initiation of the IP and continuing beyond the initiation of the IP, or those medications/procedures started at the same time or after the initiation of the IP will be denoted "Concomitant".

Medications/procedures will be presented according to whether they are "Prior" or "Concomitant" as defined above. If medication/procedures dates are incomplete and it is not clear whether the medication/procedures are concomitant, it will be assumed to be concomitant.

Missing or partial dates will be imputed for medication/procedures. Algorithm for missing or partial start /end date is documented in [Appendix C](#).

Concomitant medications/procedures are further categorized as on-treatment and post-treatment as follows:

1. On-treatment concomitant medications/procedures are those that have been used between first and last dose of IP (both inclusive) as well as medications started prior to first dose of IP and continue beyond the initiation of IP.
2. Post-treatment concomitant medications/procedures are those that have been started after the last dose of IP.

Concomitant medications and concomitant procedures will be summarized on Safety Set using ATC level 1 and preferred term by actual treatment group. By-participant listings of prior and concomitant (on-treatment and post-treatment) medications, and concomitant procedure will also be provided.

### **8.2.6. Physical Examination**

This analysis will be based on the Safety Set.

Full physical examinations will be performed at Screening and Day 112 (or ET), and include assessment of body system (e.g., head, eye, ear, nose, and throat [HEENT], heart, lungs, abdomen, and extremities) as well as cognitive and neurological examination, and mental status examination. Unscheduled physical examinations may also be conducted per the Investigator's discretion. At other visits, brief physical examination will be performed including general appearance, cardiovascular, respiratory, gastrointestinal, and neurological systems. Any abnormality in physical examinations will be interpreted by an Investigator as abnormal, not clinically significant (NCS); or abnormal and clinically significant (CS) which will be reported as an AE.

By-participant listing of physical examination will be provided.

